7.8 Safety Analyses

7.8.1 Extent of Exposure

The number of subjects administered study drug and the duration of exposure to study drug will be summarized descriptively by treatment group (n, mean, median, SD, minimum, and maximum values). Extent of exposure is defined as last dose of study drug – first dose of study drug +1.

7.8.2 Treatment Compliance and Modifications

Treatment compliance for the rifaximin use will be calculated using the following algorithm:

Percent overall compliance for the rifaximin use will be calculated as: $100 * (\text{total number of tablets dispensed} - \text{total number of tablets returned}) / (4 \times \text{total extent of exposure})$ [as defined in Section 7.8.1. above].

Compliance will be defined for a subject as the receipt of at least 80% and no more than 120% of the expected tablets.

Calculated overall compliance and compliance will be summarized descriptively by treatment group (n, mean, median, SD, minimum, and maximum values). The number and percent of compliant and noncompliant subjects based on the calculated overall compliance will be summarized by treatment group.

7.8.3 Adverse Events

Adverse events will be coded using the Medical Dictionary for Regulatory Activities (MedDRA) coding dictionary. Treatment-emergent AEs will be defined as any event with a start date occurring on or after Visit 2 (Day 1) or, if pre-existing, worsening after Visit 2 (Day 1).

7.8.3.1 Treatment-Emergent Adverse Events

A non-fatal AE is considered as a treatment emergent adverse event (TEAE), if the start date of the AE is within the period of first dose date of study medication and last dose date of study medication plus five days. A fatal AE is considered TEAE if the start date of the AE is within the period of first dose date of study medication and last dose of study medication plus 30 days.

The incidence of treatment-emergent AEs will be summarized by body system and MedDRA preferred term. If a subject reports the same AE more than once, then that subject will only be counted once for the summary of that AE, using the most severe intensity.

In case of incomplete or missing AE dates, the standard Salix estimation rule for AEs will be followed in order to determine whether an AE should be considered treatment-emergent. If the AE category still can't be determined, the AE will be considered as TEAE. The onset dates reported in the CRF will be presented in the listings.

Treatment-emergent AEs will be summarized as follows:

- All treatment-emergent AEs;
- All treatment-emergent AEs by intensity;
- All treatment-emergent AEs related to study drug;
- All treatment-emergent SAEs; and

- All treatment-emergent AEs that led to premature discontinuation of study drug.

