#### **6.1.7      Visit 17: End of Study (EOS) Visit, Week 54/Day 378 ( $\pm$ 3 days)**

The following assessments are to be completed:

- Adverse events and concomitant medications
- Vital signs and weight
- Electrocardiogram
- Safety laboratory tests (hematology, blood chemistry, urinalysis)

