### **7.3.1 The Time Period for Detecting and Reporting of AEs and SAEs**

The Time Period for Detecting and Reporting of AEs and SAEs is from the time of informed consent through study completion/withdrawal, including the follow-up period.

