### **7.3.2 Post-Study SAEs**

Investigators are not obligated to actively seek SAE information in former study participants, but investigators are encouraged to notify Salix of any SAEs occurring at any time after a subject has discontinued or terminated study participation that they judge may reasonably be related to study treatment or study participation.

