7.3 Sample Size

For sample size justification, reference corresponding study protocols.

Originally planned sample sizes per arm for each of the studies are listed below:

Study	Treatment A: Rifaximin DR Tablets 800 mg BID	Treatment B: Placebo BID
RECD3125	330	330
RECD3126	330	330

Both studies will be terminated early therefore the actual sample size may vary.

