8 CHANGES FROM PROTOCOL-SPECIFIED ANALYSES

Because both studies will be terminated early and for the purpose of abbreviated CSR originally planned evaluations that will not be performed include:

Additional analysis of Secondary Efficacy Endpoints:

- Longitudinal analysis using a mixed model of the change from baseline in continuous outcomes measured at multiple post-baseline time points.
- Determination whether the declaration of response based on the co-primary endpoints for induction parallels the pattern of CDAI scores
- Comparison of changes in the CDAI scores between responders and non-responders to the co-primary endpoints via Wilcoxon rank-sum test

Analysis Exploratory Endpoints:

- Characterization of stool microbiota at baseline and after 16 and 52 weeks of treatment.
 - Baseline and post-treatment bacterial DNA isolated from stool for 16S rRNA gene amplification.
 - Descriptive characterization of bacteria in stool by:
 - Isolation and identification of selected Gramnegative and Gram-positive bacteria.
 - Resistance to selected antibiotics, including rifaximin and rifampin.
- Genomic profiling of pregnane X receptor (PXR) in blood.
- Population pharmacokinetics of rifaximin.

Clinical Laboratory Assessments:

- A summary of shifts from baseline to final evaluation for each treatment group for each parameter.

Electrocardiogram

- QT correction based on linear regression techniques

These changes will be documented in the Clinical Study Report

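### The SAP defines treatment-emergent adverse events twice, once with no end date and once closing at last dose + 5 days for non-fatal events, and does not say which definition governs

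*SAP*

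**What the plan says.** SAP 7.8.3 defines a treatment-emergent adverse event (TEAE) as "any event with a start date occurring on or after Visit 2 (Day 1) or, if pre-existing, worsening after Visit 2 (Day 1"). This is the definition in protocol 8.6.5. It has no end date and it includes worsening.

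SAP 7.8.3.1, the next paragraph, gives a different rule. A non-fatal event counts if it starts between first dose and "last dose date of study medication plus five days". A fatal event counts if it starts no later than 30 days after last dose. Worsening is not mentioned. Where dates are incomplete or missing and the category still cannot be settled, "the AE will be considered as TEAE". The list of TEAE tables follows directly.

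Other relevant places:
- Protocol 7.3.1 sets the AE collection period: "from the time of informed consent through study completion/withdrawal, including the follow-up period". The End of Study visit (protocol 6.1.7) includes "Adverse events and concomitant medications".
- Protocol 7.3.2, on the time after the study: "Investigators are not obligated to actively seek SAE information in former study participants".
- SAP 7.10.3 caps certain imputed AE start dates at last dose + 30 days, with no split between fatal and non-fatal events.
- SAP 7.3: "Both studies will be terminated early therefore the actual sample size may vary".
- SAP 8, on departures from the protocol, introduces its list with "originally planned evaluations that will not be performed include". The TEAE definition is not on it.

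**The concern.** The two paragraphs classify the same event differently, and no sentence ranks or links them. Two programmers could each follow the SAP faithfully and produce different tables. Every AE summary listed in 7.8.3.1 is restricted to TEAEs, so the choice decides whether a late non-fatal event enters the overall, intensity, related and serious-event tables or stays in the listings.

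The narrower rule also departs from the protocol. Data gathered on purpose during the two-week follow-up would mostly be left out of the summaries, and the SAP neither gives a reason nor tells the reader that the definition has changed.

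Events after the drug is stopped are of some interest for this product. Protocol 1.4 reports one *C. difficile* infection diagnosed 20 days after treatment ended in a Phase 2 patient on 800 mg twice daily. This only illustrates the point: diagnosis is not onset, and 20 days is beyond the follow-up planned here.

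**Working it through.** There is no stated figure to reproduce. The check compares the two rules and counts days.

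**Rules side by side**

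| Event (known start date) | SAP 7.8.3 / protocol 8.6.5 | SAP 7.8.3.1 |
|---|---|---|
| Non-fatal, starts 5 days after last dose | TEAE | TEAE |
| Non-fatal SAE, starts 8 days after last dose | TEAE | not a TEAE; listings only |
| Fatal, starts 8 days after last dose | TEAE | TEAE |
| Pre-existing, worsens on treatment, original start date kept | TEAE | not a TEAE |

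The default for undetermined events in 7.8.3.1 does not rescue the second row, because it applies only to incomplete or missing dates.

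**Completers, nominal schedule**
- Last dose is the evening before Visit 16 (protocol 6.1.6). Visit 16 is Day 364, so last dose is Day 363.
- Non-fatal cut-off: 363 + 5 = Day 368.
- End of Study: Day 378 (protocol 6.1.7).
- Post-dose days: 378 − 363 = 15. Excluded days: 378 − 368 = 10 (Days 369 to 378).
- Share of Days 1 to 378: 10/378 = 2.6%.

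**Completers, ±3-day visit windows**
- Fewest excluded: Visit 16 on Day 367, last dose 366, cut-off 371, End of Study on Day 375. Post-dose days 375 − 366 = 9; excluded 375 − 371 = 4.
- Most excluded: Visit 16 on Day 361, last dose 360, cut-off 365, End of Study on Day 381. Post-dose days 381 − 360 = 21; excluded 381 − 365 = 16.

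**Early discontinuers followed for 14 days** (protocol 4.5, where this follow-up is only to be attempted)
- Excluded days: 14 − 5 = 9 of 14, or 64%.

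**Fatal events**
- 363 + 30 = Day 393, which is 393 − 378 = 15 days after the nominal End of Study. Fatal events starting in that stretch reach the database only through voluntary reports.

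**Start-date cap in SAP 7.10.3**
- The + 30-day cap matches the fatal window only. A non-fatal event whose imputed start is capped at last dose + 30 lies 25 days outside the non-fatal window (30 − 5). Under 7.8.3 there is no end date for the cap to match.

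**The case against.** The best defence is that 7.8.3.1 is the operational version of 7.8.3. It sits beneath it, carries the TEAE title and stands directly above the table list, and protocol 8.0 leaves algorithms and data-handling conventions to the SAP. Most programmers would probably use the dated rule. That is a fair guess about what will be run, but the SAP does not say it, and 7.8.3.1 reclassifies events where a refinement would only clarify them. If the guess is right, the fault becomes an undeclared narrowing of the protocol definition.

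Several stronger readings are tempting, and the documents do not support them.
- *Section 8 conceals the change.* Its list covers evaluations that will not be performed, and it is worded as non-exhaustive. TEAE tables will be produced, so its silence is only supporting evidence. No other part of the SAP declares the change either.
- *Serious events disappear.* They do not. SAP 7.1 puts all data in listings, and SAP 7.8.3.4 reconciles SAEs with the safety database. Only the summary tables are affected.
- *Early termination makes the loss large.* The 9-of-14 share applies to anyone who stops early and is followed for 14 days. The documents give neither the distribution of stop days nor how many subjects stop drug because of the termination.
- *A + 5-day window is wrong in itself.* A limited window can be a legitimate choice if it is declared.
- *Worsening events will be lost.* That happens only if a worsening keeps its original start date. The documents set no such convention, and protocol 7.1.1 lets a worsening be an AE in its own right.

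**Conclusion.** The point holds as an internal contradiction and an undeclared departure from protocol 8.6.5. If 7.8.3.1 is applied, non-fatal AEs and SAEs starting 6 or more days after last dose are left out of the summary tables. That is 10 of 15 post-dose days for completers on the nominal schedule (4 of 9 to 16 of 21 across the visit windows) and 9 of 14 for discontinuers followed for 14 days.

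These figures rest on the scheduled visits, on last dose the evening before Visit 16, and on the 14-day follow-up taking place. They are shares of days. The documents give no event rates for follow-up, so the number of events affected is unknown and may be small. A reader might infer biased safety results, but both rules apply equally to the two arms, so no between-arm bias is shown. No efficacy endpoint is touched. The correction should still be made, because the main AE and SAE tables ought to be reproducible from the SAP.

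**What to change.** Use one TEAE definition for all AE and SAE tables. There are two acceptable routes.

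1. Apply the protocol 8.6.5 wording, including worsening and with no added end date, to all collected AEs, and delete the window sentences in SAP 7.8.3.1.
2. Keep the + 5-day and + 30-day windows, declare them in SAP 8 as a change from protocol 8.6.5, restore the worsening clause, and tabulate by arm the AEs and SAEs that start after the window.

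On either route, bring the last dose + 30-day cap on AE start dates in SAP 7.10.3 into line with the chosen definition.

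The cost is SAP wording plus one derivation (route 1) or one extra table (route 2). Compared with tables built on 7.8.3.1 as it stands, AE counts can only stay the same or rise.

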7.8.3.2 Treatment-Emergent Adverse Events by Intensity

Adverse events are categorized for severity by the investigator as “Mild”, “Moderate” or “Severe”. The frequency of TEAEs by intensity will be summarized by body system, and preferred term, overall and by treatment group. TEAEs with missing intensity will be considered ‘Severe’ in the tabular summaries but data listings will show severity listed as missing. In case of multiple TEAEs for the same body system and preferred term for the same subject, only the TEAE with the maximum intensity will be counted in the table.

7.8.3.3 Treatment-Emergent Adverse Events Related to Study Drug

Related AEs are the AEs with “related” for causality. TEAEs with missing relationship to study drug will be considered “related” in the tabular summaries but data listings will show relationship as missing.

7.8.3.4 All Treatment-Emergent Serious Adverse Events by Intensity

Any AE reported as serious in CRF will be reported as a SAE. The clinical database will be reconciled with the serious adverse event database (from the Salix Safety department) before database lock.

All treatment-emergent SAEs will be summarized by body system and preferred term, overall and by treatment group.

7.8.3.5 Treatment-Emergent Adverse Events Leading to Study Premature Discontinuation

All TEAEs that led to subject discontinuation from the study will be summarized and listed separately.

7.8.4 Clinical Laboratory Evaluations

Laboratory values will be summarized at baseline and at each time point. In addition, changes from baseline to last visit will be summarized.

All potentially clinically significant values for clinical laboratory tests will be assessed by the investigator. Out of range laboratory values that may be potentially clinically significant will be flagged for review.

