**6.1.6        Visit 16: End of Treatment (EOT) Visit, Week 52/Day 364 (± 3 days)**

The subject's final dose of study drug will be the evening before Visit 16. The following assessments are to be completed at this visit:

- Adverse events and concomitant medications
- Vital signs and weight
- Electrocardiogram
- Full physical examination including disease specific examination (including assessments for abdominal mass and extraintestinal manifestations of Crohn's disease based on CDAI – see Appendix 2).

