4.4 Safety Endpoints

- Incidence, intensity, and types of adverse events (AEs).
- Changes from baseline in the laboratory parameters (hematology, clinical chemistry, urinalysis).
- Change from baseline in vital sign measurements.

[figure not shown]

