7.8.6 Vital Sign Measurements

Vital sign measurements will be summarized at baseline and at each time point. For each summary the number, mean, median, standard deviation, minimum, and maximum values will be presented by treatment and study phase.

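### SAP 7.8.4 measures laboratory change only to an undefined last visit, literally the off-drug Week 54 visit for completers, and SAP 7.8.6 gives no change analysis for vital signs

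*SAP*

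**What the plan says.** SAP 4.4 names two relevant safety endpoints: "Changes from baseline in the laboratory parameters (hematology, clinical chemistry, urinalysis" and "Change from baseline in vital sign measurements". Neither carries a time point.

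For laboratory tests, SAP 7.8.4 plans two summaries. The first is of levels: "Laboratory values will be summarized at baseline and at each time point". The second is of change: "In addition, changes from baseline to last visit will be summarized". Protocol 8.6.6 has the same pair. Neither document says which visit counts as last. SAP 7.8.4 also has out-of-range values that may matter clinically flagged for review.

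The schedule places laboratory samples on both sides of the last dose. Protocol 6.1.6 (Visit 16, Week 52, Day 364) states: "The subject's final dose of study drug will be the evening before Visit 16", and samples are drawn at that visit. Protocol 6.1.7 (Visit 17, Week 54, Day 378) again lists "Safety laboratory tests (hematology, blood chemistry, urinalysis", after the two-week period without study drug. Protocol 4.5 asks that early stoppers also be followed to an End of Study assessment about 14 days after their last dose.

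SAP Section 8 lists, among evaluations that will not be done, "A summary of shifts from baseline to final evaluation for each treatment group for each parameter".

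For vital signs, SAP 7.8.6 says: "Vital sign measurements will be summarized at baseline and at each time point". Protocol 8.6.7 also planned change from baseline to the last visit. SAP 7.8.6 omits it, and Section 8 does not list the omission.

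**The concern.** The laboratory endpoint is a change, and the SAP delivers it through a single comparison whose end point is not fixed. On the literal reading, a completer's value is taken when neither arm is on study drug. An effect on liver enzymes, renal function or blood counts that recovers after stopping would then look smaller in the change table than it was during treatment, and the arms would look more alike. For a safety summary after up to 52 weeks of exposure, that is the wrong direction in which to err.

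The table would also be heterogeneous. Early stoppers who return for the End of Study visit contribute an off-drug value, while those who do not return contribute whatever came before. If return rates differ between arms, so does the mix. Because the term is undefined, two programmers could also produce different tables from the same data.

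The vital-sign gap is a separate matter and does not depend on how the last visit is read: a named endpoint has no stated analysis, and its removal is not declared.

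**Working it through.** **Inputs.** Visit 16 is Day 364 ± 3 and the last dose is the evening before it (Protocol 6.1.6). Visit 17 is Day 378 ± 3 (Protocol 6.1.7). The drug-free follow-up is two weeks (SAP 5.1). A non-fatal event counts as treatment-emergent up to last dose plus five days (SAP 7.8.3.1).

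**1. The plan's own figure.** 378 − 364 = 14 days = 2 weeks, which matches the stated follow-up.

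**2. Time off drug at Visit 17.** The nominal last dose is on Day 364 − 1 = Day 363.
- Nominal: 378 − 363 = 15 days.
- Shortest: Visit 17 on Day 375, Visit 16 on Day 367, last dose on Day 366; 375 − 366 = 9 days.
- Longest: Visit 17 on Day 381, Visit 16 on Day 361, last dose on Day 360; 381 − 360 = 21 days.

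The Visit 16 sample, by contrast, is taken the day after the last dose.

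**3. Against the SAP's own adverse event rule.** Even the shortest interval, 9 days, exceeds 5 days. A non-fatal event starting at a completer's Visit 17 would not count as treatment-emergent under SAP 7.8.3.1. Yet, read literally, that visit's sample would supply the laboratory change.

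**4. Where laboratory data exist.** The on-treatment samples after baseline are at Weeks 2, 4, 8, 12, 16, 20, 24, 28, 32, 36, 40, 44, 48 and 52: 14 time points. There is one off-treatment time point, Week 54.

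**5. Possible dilution.** The documents give no rate of recovery, so this step rests on an assumption. If an effect decays exponentially after the last dose with half-life h days, the share left after t days is 2^(−t/h).

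| Assumed h (days) | t = 9 | t = 15 | t = 21 |
|---|---|---|---|
| 3 | 13% | 3% | 1% |
| 7 | 41% | 23% | 13% |
| 14 | 64% | 48% | 35% |
| 30 | 81% | 71% | 62% |

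At the nominal 15 days, 3% to 71% of the effect remains, so 29% to 97% is lost from this summary. The width of that range shows that the documents do not determine the size.

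**6. Vital signs, side by side.** SAP 4.4: change from baseline is an endpoint. Protocol 8.6.7: values at each time point, plus change to last visit. SAP 7.8.6: values only. SAP Section 8: no entry for vital signs. The endpoint and its analysis do not match, and the departure from the protocol is undeclared.

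**The case against.** The strongest reply is that this concerns one descriptive table, while the safety evaluation has several other views of on-treatment data. Levels are summarised at all 14 on-treatment time points, and SAP 7.1 adds the minimum and maximum, so extremes show. With 1:1 randomisation, the difference between arms in mean level at a visit estimates much the same contrast as the difference in mean change. All data are listed by subject (SAP 7.1), possibly significant values are flagged (SAP 7.8.4), and Protocol 7.2 requires clinically significant abnormalities that meet the definition to be recorded as adverse events.

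Most of this stands, and it rules out several stronger readings:

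- *Reversible harm would be missed.* The documents do not support this; the routes above remain open.
- *Week 54 is the rule for every completer.* It is the literal reading, but the term is undefined and the last on-treatment visit is not excluded.
- *A fixed share of the effect is lost.* Any such figure comes from assumed half-lives.
- *Dropping the shift table removed on-treatment information.* That table ran to the final evaluation (Protocol 8.6.6), which has the same ambiguity, and its removal is declared in Section 8.
- *No other laboratory change is analysed.* SAP 7.7.2.3 covers change in CRP and other inflammation markers, as efficacy outcomes. The point concerns safety laboratory tests.

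The reply does not dispose of the core. Summaries of levels are not within-subject changes, which is what the endpoint names, and the subjects contributing can differ between visits. Pairing each subject with their own baseline removes differences in starting level, although it does not cure selective dropout. Nor does the reply touch the vital-sign gap.

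**Conclusion.** The point holds in limited form. The one safety-laboratory change that SAP 7.8.4 specifies ends at an undefined visit. Read literally, that visit falls 15 days (9 to 21) after a completer's last dose, and it is also off drug for early stoppers who attend the End of Study visit. That summary can understate reversible effects and can mix on-drug with off-drug values.

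The interval follows from the visit schedule. The amount of dilution does not: the 3% to 71% remaining at day 15 assumes exponential recovery with half-lives of 3 to 30 days. The number of subjects affected is also unknown, because SAP 7.3 says both studies stop early and Protocol 4.5 asks only for an attempt at End of Study follow-up.

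The missing vital-sign change is a plain inconsistency between SAP 4.4, 7.8.6 and Section 8 and needs no assumption.

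Neither matter affects the efficacy conclusions. Both should be corrected, because the endpoints are named, the data are already collected and the remedy is cheap.

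**What to change.** In SAP 7.8.4, replace the last visit with the last on-treatment value: the Visit 16 (end-of-treatment) sample for completers, otherwise the last sample on or before the day after the last dose. Summarise change from baseline at each scheduled on-treatment visit. Report Week 54, and the End of Study samples of early stoppers, separately as off-drug follow-up.

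In SAP 7.8.6, add change from baseline in vital signs on the same rule, so that the endpoint in 4.4 has an analysis.

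A shift table from baseline to the worst on-treatment value would be an optional addition. Neither document planned one, so it would not restore anything.

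The cost is a revision of two SAP sections and a few more tables in the abbreviated report. No new data are needed.
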